11.1.3 Presentation of Results

Parasitaemia data will be listed for all enrolled subjects and summarised for the PD population. PD parameters will be presented for all subjects included in the PD population.

Parasite life-stage data (pfs25, pfMGET and sbp1 qRT-PCR) will be listed by participant and timepoint.

A full report on the pharmacodynamic data analysis will be included in the appendices of the CSR. This report will include a listing of PD endpoints (PRR_{48} , $PC_{t1/2}$), a table for Summary of PD endpoints by dose group and a figure for individual log-parasitaemia regression fit

List of planned tables, listings and figures are in Appendix, Table A.

11.2 PK Analysis

Analysis Set: PK Analysis Set

11.2.1 Source of data

Blood concentration of Pyronaridine, treatment and blood sampling information will be recorded and merged to produce PK concentration data for analysis.

11.2.2 Imputation of Non-Numerical or Negative Values

The imputation of non-numerical or negative values reported in the input data set will be performed as follows:

- Pre-dose sample times will be entered as zero
- Values that are below the limit of quantification (BLQ) obtained prior to the C_{max} will be entered as zero
- Values that are BLQ after the C_{max} will be treated as missing
- Pharmacokinetically plausible concentration value(s) below LLOQ at time points between two measurable concentration values are replaced by the LLOQ/2 value, flagged and included in the PK evaluation. In the event of an anomalous below LLOQ result mid profile, the data will be interrogated by the pharmacokineticist and raised with the client before being altered.
- Should partial AUCs be required then values that are BLQ after C_{max} may be imputed as zero for these partial areas if lambda-z cannot be determined
- Values that are quantifiable after at least 2 consecutive BLQ values after C_{max} will be treated as missing for the calculation of PK parameters
- Actual time from dose administration will be used for parameter estimation except for the pre-(first) dose data point which will be set to the nominal time of 0 hour. Data with missing time information will be discarded.
- Values that are reported as "No Result" or "No Sample" etc. will be treated as missing

11.2.3 Rules for Pharmacokinetic Parameter Estimation using WinNonlin

Blood concentration vs time profiles of pyronaridine will be generated for each subject. Pharmacokinetic parameters will be estimated using standard Phoenix WinNonlin methods, details of which may be found in the documentation accompanying the WinNonlin software package. The following constraints will apply:

Parameter Estimation	Constraint
Trapezoidal Method	Linear trapezoidal linear/log interpolation method
Number of Points used for Lambda-z	At least 3, not including C_{max}
Minimum Requirements for AUC	At least 3 consecutive quantifiable concentrations
Dose	As supplied
Sampling Times	Actual sampling times (for final analysis)

Where possible, the elimination rate constant (lambda-z) will be calculated for all subjects. The value of lambda-z will be determined by the slope of the regression line of the natural log transformed concentrations vs time.

The choice of data points for determination of lambda-z will be applied by the Phoenix software as a default method, the pharmacokineticist who may adjust the selection to provide a more appropriate fit and records of this will be documented in the software data.

11.2.4 Data Quality

The following flags/footnotes may be applied to the pharmacokinetic parameters:

Flag	Footnote
a	Rsq of regression was <0.8
b	Period used for regression analysis was less than 2-fold the calculated half-life
c	Extrapolated portion of AUC_{0-inf} >20%
d	Insufficient post- C_{max} data points for estimation of lambda-z
e	Entire profile BLQ, no pharmacokinetic parameters could be calculated
f	Regression could not be fitted

11.2.5 PK parameters

The following parameters will be estimated:

CDISC Term	Parameter	Definition	DP or SF	No. of DP/SF
TMAX	T_{max}	Time of maximum observed concentration	DP	2
TLAG	T_{lag}	The delay between time of dosing and the appearance of concentration	DP	2
CMAX	C_{max}	Maximum observed concentration	SF	3
AUCLST	AUC_{last}	Area under the curve from 0 time to the last measurable concentration	SF	3
AUCIFO	AUC_{0-inf}	Area under the curve from 0 time extrapolated to infinity	SF	3
LAMZHL	$t_{1/2}$	Apparent elimination half-life	DP	2
LAMZ	Lambda-z	Slope of the apparent elimination phase	DP	4

CDISC Term	Parameter	Definition	DP or SF	No. of DP/SF
CLFO	CL/F	Total body clearance after extravascular administration	SF	3
VZFO	V _d /F	Apparent volume of distribution based on the terminal phase after extravascular administration	SF	3

DP=decimal places

SF=significant figures

11.2.6 Presentation of Results

All bioanalytical data will be listed and summarised according to the nominal sampling timepoint.

All pharmacokinetic parameters generated will be listed and summarised. Where pharmacokinetic data fails to meet the defined criteria in Section 11.2.4. (Data Quality) the affected results will be excluded from the descriptive statistics will be flagged as per exclusion reason.

Bioanalytical and PK Parameters Listings

All bioanalytical and pharmacokinetic NCA parameters generated will be listed in individual tables according to the analyte and treatment. The data listings will be generated as defined by the PK Concentration population.

Bioanalytical and Pharmacokinetic Summary Tables

Bioanalytical and PK parameters summary tables will be performed by SSR.

Summary statistics (i.e., mean, median, SD, CV%, minimum, maximum, n, geometric mean, geometric SD and geometric CV%) will be calculated for PK results for each time point, parameter and treatment.

All summary statistics (i.e., mean, median, SD, CV%, minimum, maximum and n) will be presented for all PK parameters for blood by treatment. Also, geometric mean, geometric SD and geometric CV% will be presented for all PK parameters (except T_{max}) by treatment. The T_{max} summary statistics will be provided as n, minimum, median, and maximum only.

All the data summary tables will be generated as defined by the PK Analysis Set. Additional summary tables might be produced if required and requested.

Bioanalytical and Pharmacokinetic Figures

All arithmetical mean blood concentration vs. time curves will be produced by treatment on both linear/linear and \log_{10} /linear scales.

All spaghetti plots of individual blood concentrations against nominal sampling times after dosing for each treatment will be produced on both a linear/linear and \log_{10} /linear scale. Each volunteer's concentration profile will be represented on these plots with a different symbol and a legend will be included on the plots to define the symbols used.

List of summary tables, listings and figures are in Appendix, Table A.

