^j Blood samples for drug concentration measurements will be collected following pyronaridine treatment at 1, 2, 3, 4, 6, 8, 12, 16, 20, 24, 30, 36, 42, 48, 60, 72, 84 and 96 hours. As outpatients, blood will be collected on the following days: 13, 15, 17, 20, 22, 24, 27, 29, 32, 39, 44, 47 and 50. Allowed time windows for sample collection are specified in Section 8.4.

^k Blood samples for parasite viability ex vivo growth will be collected following pyronaridine treatment at 4, 8, 12, 16, 20, 24, 48, 72 and 96 hours.

^l Perform SARS-CoV-2 testing at the eligibility visit (NPA PCR), or at the screening visit if this visit is conducted two days prior to inoculation, Day 0 (RAT), Day 6am (NPA PCR) and Day 8 (RAT). Further details are specified in Section 8.3.7.

^m Blood samples for future malaria research will be collected during the outpatient monitoring phase on Days 15±1 and 29±1

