development to reduce the risk of selecting for resistant mutants and to target multiple stages of the parasite lifecycle including the transmissible gametocytes [5]. Further, using a combination of two or more drugs is typically considered a prerequisite for achieving cure without the need for an extended dosing regimen, which would pose compliance challenges. In the case of ACTs, the fast acting artemisinin component rapidly reduces the parasite burden, while a partner drug with a more moderate rate of action but longer elimination half-life is relied upon to clear residual parasites and prevent recrudescence. The rate of action of pyronaridine in clearing malaria parasitaemia in humans is unclear; however clinical pharmacokinetic studies have demonstrated that it has a relatively long elimination half-life of approximately 14 days [3] and thus may be able to offer extended protection from recrudescence.

Volunteer infection studies (VIS) using the induced blood stage malaria (IBSM) model have previously successfully characterised the PK/PD relationship of several experimental antimalarial compounds as well as antimalarial drugs currently in use [6-9]. The IBSM model involves intravenous inoculation of healthy adult participants with blood-stage parasites and administration of the test antimalarial when parasitaemia reaches a predefined threshold. Frequent blood sampling is performed to measure parasitaemia and drug concentration kinetics over the course of the study, thus providing data for PK/PD modelling analyses. Such VIS have been shown to accurately predict the activity of investigational antimalarials in studies in endemic populations [10,11].

The current study aims to determine the PK/PD relationship of single doses of pyronaridine following administration in healthy adult participants using the *P. falciparum* IBSM model. Data obtained in this study will support the use of pyronaridine in new antimalarial combination therapies by informing partner drug selection and dosing considerations.

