4.2 SCIENTIFIC RATIONALE FOR STUDY DESIGN

The study design of this trial using the IBSM model has been used previously to safely and effectively determine the PK/PD relationship of several antimalarial agents [6-9]. The *P. falciparum* 3D7 challenge agent used to initiate blood-stage malaria infection in this study has been well characterised, with consistent and reproducible parasite growth occurring following intravenous inoculation of healthy participants in previous studies. Experience from these studies indicates that parasitaemia will be above 5,000 parasites/mL on Day 8 following inoculation, but clinical symptoms of malaria will either be absent or only mild in severity.

The duration of confinement within the clinic following dosing with pyronaridine on Day 8 (96 hours) is considered appropriate to ensure close monitoring of participants for safety purposes and to enable frequent blood sampling for parasitaemia and drug concentration measurements. Blood sampling time points have been selected by taking into account data from previous clinical PK studies, as well as

preclinical data on the antimalarial activity of pyronaridine. These time points may be adjusted during the study, by means of a protocol amendment, based on the emerging data in order to optimally determine the exposure/response relationship of pyronaridine.

The total follow-up period following pyronaridine dosing (42 ± 2 days) is equal to three times the elimination half-life of pyronaridine (approximately 14 days). This duration was selected to allow sufficient time for pyronaridine blood concentrations to fall to a level amenable to parasite regrowth, which is required to calculate the PK/PD parameters. Further, this duration will ensure that participants have a negligible blood concentration of the IMP at the completion of the study.

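### The SAP drops non-compartmental results whose regression span is under two half-lives, so with 42 days of sampling long half-lives are selectively removed and the summarised t1/2 is biased downward

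*SAP*

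**What the plan says.** SAP 11.2.4 lists six quality flags for the non-compartmental analysis. Flag b reads "Period used for regression analysis was less than 2-fold the calculated half-life". Flag a is a regression R-squared below 0.8, and flag c is "Extrapolated portion of AUC_{0-inf} >20" percent. Flags d, e and f cover cases where lambda-z or the whole profile cannot be evaluated. SAP 11.2.6 gives the consequence of failing a criterion: "the affected results will be excluded from the descriptive statistics". All parameters are still listed individually, with the reason for exclusion. No summary that includes flagged values is specified.

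Protocol 2.1 describes a "relatively long elimination half-life of approximately 14 days", and Protocol 4.2 says the 42 ± 2 day follow-up after dosing "is equal to three times the elimination half-life of pyronaridine (approximately 14 days". Dosing is on Day 8. Outpatient PK samples are on Days "13, 15, 17, 20, 22, 24, 27, 29, 32, 39, 44, 47 and 50" (Protocol 1.3). Protocol 9.4.3 plans summaries of all PK variables and mentions no exclusion based on regression span. SAP 13 declares no change to the planned analysis.

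**The concern.** A quality rule should remove unreliable results without regard to the direction of the answer. Flag b compares the regression span with twice the half-life being estimated. For a given span, a short half-life passes and a long one fails. With follow-up of only three expected half-lives, the cut-off lies close to the expected value, so it cuts into the main body of the distribution and not only its far tail.

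The long half-life is the protocol's stated reason why pyronaridine might protect against recrudescence (2.1), and the non-compartmental PK parameters are a named secondary endpoint. There are at most 18 participants, with two per dose group in the proposed Cohort 1, so losing one value can halve a group summary. The SAP also does not say whether flag b removes only t1/2 and lambda-z, or AUCinf, CL/F and Vz/F as well.

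**Working it through.** **Inputs from the documents.** Expected half-life 14 days (Protocol 2.1, 4.2). Last PK sample on Day 50, dosing on Day 8 (Protocol 1.3). Flag b threshold 2 × t1/2 (SAP 11.2.4).

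**Plan's own figure.** Day 50 − Day 8 = 42 days, and 42 / 14 = 3 half-lives. This reproduces Protocol 4.2.

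**Cut-off.** If the terminal fit starts *s* days after dosing and runs to the last sample, a result passes flag b only if t1/2 ≤ L = (42 − s)/2. With the +2-day window and a start at dosing, L = 44/2 = 22 days. Nothing longer can enter the summary.

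**Size for t1/2.** The documents give no between-participant variability, LLOQ or lambda-z start. I therefore assume a log-normal t1/2 with median 14 days, estimated without error, with quantifiable samples to day 42.
- σ = √ln(1 + CV²); for CV 30%, σ = 0.294.
- z = ln(L/14)/σ; share excluded = 1 − Φ(z).
- Retained geometric mean = 14 × exp(−σλ), with λ = φ(z)/Φ(z).
- Retained log-variance = σ²(1 − zλ − λ²).

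Example, start on day 7: L = 17.5; z = ln(1.25)/0.294 = 0.76; excluded 22%; λ = 0.385; geometric mean = 14 × exp(−0.113) = 12.5 days.

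| Fit start (days post-dose) | Longest t1/2 passing (d) | Excluded, CV 30% | Expected of 18 | Retained geometric mean (d) | Bias | Retained CV |
|---|---|---|---|---|---|---|
| 0 | 21.0 | 8% | 1.5 | 13.3 | −5% | 26% |
| 4 | 19.0 | 15% | 2.7 | 12.9 | −8% | 24% |
| 7 | 17.5 | 22% | 4.0 | 12.5 | −11% | 22% |
| 14 | 14.0 | 50% | 9.0 | 11.1 | −21% | 18% |

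Over CV 20–50% and these starts, exclusion runs from 2% to 50% and bias from −1% to −31%. At CV 20% with a day 4 start, 6% are excluded and the mean is 13.65 days (−2.5%).

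**Groups of two.** The chance that at least one of two values is dropped is 1 − (1 − p)². At CV 30% this is 28% for a day 4 start (p = 0.15) and 75% for a day 14 start (p = 0.50).

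**Flag c.** For a mono-exponential profile the extrapolated share at 42 days is 2^(−42/t1/2). It is 12.5% at 14 days and passes 20% when t1/2 > 42 × ln 2 / ln 5 = 18.1 days. Flag c therefore also selects against long half-lives, but less strictly than flag b unless the fit starts early.

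**Simulated analysis on the protocol sampling times.** Assumptions: biexponential profile, terminal t1/2 14 days, distribution half-life 1.5 days, residual error 5–15%, lambda-z points chosen by best adjusted R-squared with at least three points, no LLOQ. Flag b failed in 36–61%. The true geometric mean t1/2 was 10.9–13.1 days in those kept and 15.4–16.9 days in those dropped. Estimated geometric means, kept against all, changed as follows:

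| What varies between participants | t1/2 | AUCinf | CL/F | Vz/F |
|---|---|---|---|---|
| CL only (log-SD 0.3) | −4 to −19% | −6 to −19% | +6 to +23% | 0 to +2% |
| V only (log-SD 0.3) | −3 to −18% | 0 | 0 | −4 to −18% |
| Both (log-SD 0.25 each) | −5 to −22% | −4 to −11% | +4 to +13% | −2 to −12% |

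Only the t1/2 direction is the same in all three.

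**The case against.** The rule has a legitimate purpose: a half-life fitted over less than two half-lives is imprecise, and in a group of two one bad value can dominate. SAP 11.2.4 is also permissively worded ("The following flags/footnotes may be applied to the pharmacokinetic parameters"), individual values stay in the listings, n is reported, and SAP 11.2.6 allows further summary tables on request. These are descriptive secondary tables. The primary analysis is a population model that censors values below the LLOQ and has no span rule, and Protocol 9.4.2 already tabulates population PK estimates with their relative standard errors. All of this stands and limits the consequence. It does not remove the selection, because the exclusion sentence in 11.2.6 is not permissive and no all-values summary is committed to.

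A second objection is that the usable span is not common to everyone. SAP 11.2.2 treats values below quantification after Cmax as missing, so low doses or fast elimination shorten the span, and removal is then not purely of long half-lives. That is right, and the LLOQ is not given. In one simulated case with an assumed LLOQ of 2% of Cmax, 78% failed flag b, yet those kept still had the shorter true half-life (geometric mean 11.0 against 14.8 days).

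Three stronger readings are tempting but unsupported.
- A reader might infer that a typical 14-day participant is excluded. That participant passes if the fit starts by post-dose day 14 (Day 22).
- A reader might infer that AUCinf, CL/F and Vz/F are all biased. AUCinf and CL/F move only to the extent that CL varies, and Vz/F mainly if V varies; the documents say nothing about either.
- A reader might infer that most values would be lost. Analytically, that needs fits starting later than day 14 (84% at CV 30% from day 21), which nothing in the SAP implies. The simulation reaches 61%, but only under its own assumptions.

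**Conclusion.** The point holds for t1/2. The rule truncates on the quantity being estimated, no half-life above 21 days (22 with the visit window) can be summarised, and the cut-off falls to 14–19 days for fits starting 14 to 4 days after dosing. The summarised t1/2 and its spread are biased downward. The direction follows from the documents' own figures when samples are quantifiable to the last visit. The size does not: it may be a few percent or, with a late fit start, a fifth or more. For AUCinf, CL/F and Vz/F the bias is conditional on the source of variability and on whether flag b is read as removing them. Cmax, Tmax, AUClast and the primary population PK/PD model are unaffected. This is a correctable weakness in a secondary endpoint and no threat to the primary objective.

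**What to change.** In SAP 11.2.6, exclude outright only results that cannot be calculated (flags d, e and f). For flags a, b and c, present the lambda-z-dependent parameters (t1/2, lambda-z, AUCinf, CL/F and Vz/F) twice: once with all calculable values, flagged, and once with the flagged values removed, giving n for each. In 11.2.4, state which parameters each flag affects. Interpret t1/2 from the all-values summary beside the population-PK estimate already planned.

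The cost is SAP wording and one extra table, with no new data. The downside is that some imprecise individual values enter the all-values summary; the flags and the restricted summary next to it keep that visible.

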11.3 Safety

Analysis Set: Safety data will use both FAS and IMP Sets

Safety and tolerability will be assessed by clinical review of the following parameters:

- Adverse events (AEs)
- Vital signs
- 12-lead ECG
- Haematology, biochemistry, urinalysis
- Physical examination

11.3.1 Adverse Events

AEs will be separated into two categories.

- Inoculum-emergent AEs (IEAEs)= AEs beginning any time from inoculation with the challenge agent until the end of study.
- Treatment-emergent AEs (TEAEs)= AEs beginning any time from administration of the IMP until the end of study.

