Transient, asymptomatic liver function test (LFT) abnormalities, including rare cases of alanine aminotransferase (ALT) and/or aspartate aminotransferase (AST) elevations >10 fold the upper limit of normal (\times ULN), have been reported in several participants in IBSM studies. However, changes in bilirubin have only been reported in one participant with unappreciated pre-existing liver disease. The LFT abnormalities did not require treatment, and resolved by the end of the studies. A few cases of the LFT elevations were considered serious AEs (SAEs) by two Pharma sponsors due to internal processes for SAE notifications. An independent review involving drug-induced liver injury experts found these liver function abnormalities are most likely a direct consequence of the malaria infection rather than a direct drug-induced liver injury caused by an investigational antimalarial drug. As a precaution, all participants with LFTS above ULN will be excluded in this trial. All enrolled participants will undergo regular safety monitoring to assess for asymptomatic liver function abnormalities. Participants will be required to minimise intake of possibly hepatotoxic substances, such as alcohol and paracetamol, during the trial. Drugs of abuse are not permitted under any circumstance. Given the fact that pyronaridine has also been associated with LFT abnormalities, participants with an ALT or AST $> 2 \times$ ULN, or a total bilirubin $> 1 \times$ ULN, will be dosed with compulsory antimalarial treatment rather than pyronaridine (see above, “Risks associated with IMP [pyronaridine]”).

Risk management of cardiac adverse events

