8.1.7 ANTIMALARIAL RESCUE TREATMENTS

All participants will receive compulsory antimalarial rescue treatment with Riamet® on Day 47±2, or earlier in the following cases:

- Parasitaemia is not reduced by approximately 10-fold at the end of the 96 hour confinement period (Day 12) when compared with peak parasitaemia.
- Parasite regrowth occurs after an initial reduction in parasitaemia, with regrowth defined as ≥ 5000 parasites/mL and a 2-fold parasitaemia increase within 48 hours.
- Volunteer discontinuation/withdrawal from the study (see Section 7.2).
- Investigator's discretion in the interest of participant safety.

As qPCR results are not received in real-time, rescue may occur when these parasitaemia thresholds are presumed to have occurred.

If gametocytes are present as determined by qRT-PCR at any time point after the confinement period, a single dose of Primacin® will be administered at the Investigator's discretion. A participant's G6PD status will determine the dose of primaquine administered. If an allergy or contraindication to Riamet® or Primacin® develops, Malarone® will be administered. In the rare event that a participant cannot tolerate oral drugs, participants will be admitted to hospital and I.V. artesunate will be administered.

The following procedures will be performed prior to antimalarial rescue treatment:

- Perform symptom-directed physical examination if clinically indicated.
- Obtain a 12-lead ECG.
- Record vital signs.
- Record AEs and use of concomitant medications.
- Check participant diary cards.
- Collect blood samples for
 - haematology and biochemistry,
 - malaria 18S qPCR,
 - drug concentration
- Collect sample for parasite viability *ex vivo* growth. **NOTE only if antimalarial rescue treatment is administered prior to Day 47±2.**

Please note if a participant receives antimalarial rescue treatment after administration of pyronaridine but prior to Day 47±2, drug concentration, haematology, biochemistry and future malaria research blood collection will still be required for the full duration of the trial. Following antimalarial rescue treatment blood will be taken for 18S qPCR at the completion of Riamet and until at least one negative result is obtained.

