9.4.4 SAFETY ANALYSES

All descriptive statistics for safety parameters will be evaluated using the Safety Set.

All AE data will be listed for each volunteer, including severity, relationship to IMP (pyronaridine and malaria challenge agent), relationship to non-IMP protocol-specific treatments, outcome and actions taken. In addition, listings of AEs leading to discontinuation of the study, AESIs, SAEs and deaths, will be provided as applicable. Adverse events (AE) will be coded according to MedDRA and grouped by SOC and PT.

The main AE summaries will be restricted to Treatment Emergent Adverse Events (TEAEs) only, where a TEAE is defined as an AE that commences on, or after, the first administration of IMP up to the end-of-study (EOS) visit (inclusive). TEAEs without an onset date or time will be defined as treatment emergent except if an incomplete date (e.g., month and year) clearly indicates that the event started prior to first administration of IMP, or if the AE stop date indicates that the event stopped prior to the first administration of IMP.

At a minimum, the following AE summary tables will be provided:

- Overall summary of AEs
- All TEAEs
- TEAEs by severity
- TEAEs by relationship to the IMP
- TEAEs by relationship to rescue medications
- Serious TEAEs
- TEAEs leading to study withdrawal
- AESIs
- All Inoculation Period AEs
- Inoculation Period AEs by relationship to the malaria challenge agent

Lab parameters, physical examination, Body measurements, vital signs, Beck Depression inventory score and 12-lead ECG will be listed for all participants and visits. Summary tables for each scheduled visit, including observed values, change from each baseline and clinical significance of each abnormal value, will be presented.

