11.3.1.2 AE Tables

The number of events, as well as the number and percentage of participants experiencing an AE, will be summarised by, dose group and overall as follows:

Overall summary of IEAEs (FA set)

Overall summary of TEAEs (IMP set)

Summary of IEAEs by System Organ Class and Preferred Term (FA set)

Summary of TEAEs by System Organ Class and Preferred Term (IMP set)

Summary of IEAEs by System Organ Class, Preferred Term and Maximum Severity (FA set)

Summary of TEAEs by System Organ Class, Preferred Term and Maximum Severity (IMP set)

Summary of Malaria-Related IEAEs by System Organ Class and Preferred Term (FA set)

Summary of IMP-Related TEAEs by System Organ Class and Preferred Term (IMP set)

Summary of Malaria-Related IEAEs by System Organ Class, Preferred Term and Maximum Severity (FA set)

Summary of IMP-Related TEAEs by System Organ Class, Preferred Term and Maximum Severity (IMP set)

Summary of IE SAEs by System Organ Class and Preferred Term (FA set)

Summary of TE SAEs by System Organ Class and Preferred Term (IMP set)

Overall Summary of IE AESIs (FA set)

Overall Summary of TE AESIs (IMP set)

Summary of IE AESIs by System Organ Class and Preferred Term (FA set)

Summary of TE AESIs by System Organ Class and Preferred Term (IMP set)

For the summary tables, participants who experience the same AE (in terms of the MedDRA preferred term) more than once will only be counted once.

Additional summary tables of AEs related to rescue medications will be included if requested by MMV.

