Laboratory abnormalities will be presented as cross-tabulations of the abnormality at each post-treatment baseline analysis visit versus the treatment baseline. Numbers of participants with treatment-emergent abnormalities will also be shown.

In addition, the liver function tests, namely AST, ALT, and total bilirubin, are used to assess possible drug-induced liver toxicity. The proportion of patients with Potential Clinically Significant Abnormality (PCSA) values at any post base line visit will summarized. The highest value of PCSA and time to the highest PCSA reading will also be summarized. Any of the following event will be considered as a PCSA:

- Any ALT or AST value above 5×ULN.
- An elevation in bilirubin 2×ULN.
- Any AST or ALT value above 2×ULN and (total bilirubin >1.5×ULN).
- Any AST or ALT value above 2×ULN with the appearance of fatigue, nausea, vomiting, right upper quadrant pain or tenderness, fever, rash and/or eosinophilia (eosinophil percent or count above the ULN).
- Constitutes a possible Hy's Law case
 - Hy's Law case is defined as a Participant with any value of alanine or aspartate aminotransferase greater than 3×ULN together with an increase in total bilirubin to a value greater than 2×ULN and not associated to an alkaline phosphatase value greater than 2×ULN (FDA Guidance on Drug Induced Liver Injury: Premarketing Clinical Evaluation [2009]).

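### By-dose safety tables run from dosing to end of study with no separate view of time after rescue, and the protocol's required table of rescue-related adverse events has become optional

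*SAP*

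**What the plan says.** **Adverse events.** SAP 11.3.1 defines "Treatment-emergent AEs (TEAEs)= AEs beginning any time from administration of the IMP until the end of study". SAP 11.3.1.2 then says that the "percentage of participants experiencing an AE, will be summarised by, dose group and overall". Protocol 9.4.4 uses the same window, from first IMP administration through the end-of-study visit.

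**Liver and ECG.** SAP 11.3.3 summarises "The proportion of patients with Potential Clinically Significant Abnormality (PCSA) values at any post base line visit". The SAP appendix (Table B) adds peak liver readings, and time to peak, since IMP administration. The QTcF categories in SAP 11.6 draw on scheduled and unscheduled visits alike. None of these stops or divides at rescue.

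**Sampling after rescue.** For a participant rescued early, Protocol 8.1.7 states that "drug concentration, haematology, biochemistry and future malaria research blood collection will still be required for the full duration of the trial". Post-rescue values therefore enter the laboratory tables.

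**Rescue-related events.** Protocol 9.4.4 has "TEAEs by relationship to rescue medications" in its minimum list of tables. SAP 11.3.1.2 says: "Additional summary tables of AEs related to rescue medications will be included if requested by MMV". SAP 13 reports no change to the planned analysis.

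**Onset timing.** Protocol 8.5.6 collects event onset relative to IMP, inoculation and rescue. SAP 11.3.1.1 derives it relative to IMP only. SAP 10.5, by contrast, flags parasite data obtained after first rescue.

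**The concern.** Early rescue is partly a consequence of how well the dose worked. Protocol 8.1.7 brings it forward when parasitaemia has not fallen enough by Day 12, or when parasites regrow. A dose group with more early rescue therefore has a second parasitaemia and a longer post-rescue period inside its treatment-emergent window.

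This matters most for the liver. Transaminase rise is a known risk of pyronaridine (Protocol 2.2.1). The same section reports that an independent review of earlier studies in this infection model "found these liver function abnormalities are most likely a direct consequence of the malaria infection". A liver signal during or after regrowth and one from the drug look alike in a table of any post-baseline abnormality by dose. If regrowth is commoner at lower doses, a real dose-related effect could be blurred, or a spurious inverse one suggested. Causality coding does not help here: it filters the IMP-related and malaria-related event tables, but not the tables of all treatment-emergent events, severity, serious events, AESIs, liver abnormalities, peak readings or QTcF.

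**Working it through.** **1. Reproduce the plan's follow-up figure.** Dosing is on Day 8, scheduled rescue on Day 47, end of study (EOS) on Day 50 (nominal days). 50 − 8 = 42 days, which matches Protocol 4.2. It splits as 47 − 8 = 39 days before rescue and 50 − 47 = 3 after, which matches the volunteer duration in Protocol 1.1.

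**2. Post-rescue share of the window.** Share = (50 − rescue day) / (50 − 8). The laboratory draws counted are Days 15, 22, 29, 37 and 44 (Protocol 8.1.6) plus EOS (8.1.8). Days 47 and 12 come from Protocol 8.1.7; Days 20, 29 and 39 are illustrative, because the documents give no distribution of rescue days.

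| Rescue day | Days before | Days after | Share after | Draws after, of 6 |
|---|---|---|---|---|
| 12 | 4 | 38 | 90.5% | 6 |
| 20 | 12 | 30 | 71.4% | 5 |
| 29 | 21 | 21 | 50.0% | 3 |
| 39 | 31 | 11 | 26.2% | 2 |
| 47 | 39 | 3 | 7.1% | 1 |

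The two ends differ by 38/3 = 12.7 in days.

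**3. Allow for visit windows.** With scheduled rescue on Days 45 to 49, EOS on Days 48 to 52 and at least 3 days between them (Protocol 8.1.8), the post-rescue share runs from 3/44 = 6.8% to 7/44 = 15.9%. For Day 12 rescue it runs from 36/40 = 90.0% to 40/44 = 90.9%. The contrast does not depend on nominal days.

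**4. What this can do in a small group.** Cohort 1 plans two participants per dose, so one affected participant is 50% of a group. As an illustration only, suppose pyronaridine causes no events, both participants regrow, and each regrowth episode produces at least one event with probability q. The chance that the group shows one or more such events is 1 − (1 − q)²:

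- q = 0.25: 43.8%
- q = 0.50: 75.0%
- q = 0.75: 93.8%

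The documents give no value for q.

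**5. Compare the two documents on the rescue table.** The protocol lists it as part of a minimum set, the SAP makes it conditional on a request, and SAP 13 declares no change. These three statements cannot all stand.

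**The case against.** A reader might infer that the plan attributes every event after dosing to pyronaridine. It does not. Treatment-emergent is a time window. Causality is judged separately for challenge agent, pyronaridine and rescue medication (Protocol 8.5.4.2), and SAP 11.3.1.1 lists each. IMP-related and malaria-related events have their own tables, and expected malaria symptoms with a positive qPCR are classed as related to the challenge agent.

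The window is also the stated endpoint: Protocol 3 and SAP 3.5.2.1 define safety from Day 8 to Day 50±2.

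A tempting remedy is to make dosing-to-rescue the main summary. It would do harm:

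- Regrowth starts before the rescue it triggers, so it would stay in the supposedly clean period.
- Follow-up would end at an event that may depend on dose, leaving 4 days for Day 12 rescue against 39 for Day 47.
- Protocol 2.2.1 places transaminase rises 3 to 7 days after treatment. The Day 15 draw, 7 days after dosing, would drop out for anyone rescued on Day 12.
- Post-rescue days are not free of pyronaridine. With a half-life of about 14 days, Day 12 is 4/14 = 0.29 of a half-life after dosing.

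Finally, the analysis is descriptive, with at most 18 participants. Rescue dates and event times are listed, and laboratory and ECG values are summarised by visit, so a careful reader can reconstruct each sequence.

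All of this stands against replacing the main tables. It does not answer the request for a supportive split, because a visit summary still mixes rescued and unrescued participants, and it does not explain the downgraded table.

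**Conclusion.** Two points hold. First, the SAP makes a protocol-minimum table optional without declaring it; that is wrong as written. Second, the by-dose tables for treatment-emergent events, AESIs, liver abnormalities, peak liver readings and QTcF mix pre- and post-rescue data. Post-rescue time ranges from 3 to 38 of 42 days, and a supportive split would be a cheap improvement.

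The day counts measure unequal observation. They are not an estimate of bias, and the 12.7 ratio compares two extremes. It should not be read as a ratio of drug exposure, since Riamet is compulsory for everyone. Primacin depends on gametocytes and investigator discretion, so it does not simply follow early failure.

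A reader might also infer that the lower doses are known to fail first. Protocol 4.3 says only that modelling suggests a dose as low as 180 mg may be needed for regrowth, while the groups named in SAP 4.2.4 are 360, 540 and 720 mg. An imbalance by dose is plausible in direction but not established.

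**What to change.** In the SAP:

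1. In 11.3.1.2 and appendix Table B, make the table of treatment-emergent events by relationship to rescue medications mandatory.
2. Keep the whole-period tables, Day 8 to Day 50±2, as the main summaries.
3. In 11.3.1.1, derive onset relative to first rescue dose and add a flag for before or after it. Say whether Primacin alone, which Protocol 6.5.1 counts as a rescue treatment, starts the later period.
4. Show treatment-emergent events, AESIs, liver abnormalities, peak and time-to-peak liver readings, and QTcF categories by period as supportive tables, with days at risk per dose group in each period.
5. State that regrowth symptoms before rescue remain in the pre-rescue period, so the split does not isolate pyronaridine effects.

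The cost is SAP wording, one derived flag and a few more tables. Rescue dates are already listed under SAP 7, and onset relative to rescue is already collected under Protocol 8.5.6. No new data or change in trial conduct is needed.
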